# ABBREVIATIONS AND DEFINITIONS OF TERMS

AE Adverse event

#### ABSTRACT

#### Context: (Background)

Tinnitus is a medical condition with a wide variety of causes that is characterized by the perception of sound, often described as ringing or buzzing, without an external stimulus. Venous pulsatile tinnitus is a specific subtype of tinnitus with limited treatment options beyond surgical correction of underlying vascular defect. The clinical diagnostic hallmark of venous pulsatile tinnitus is relief of symptoms with light compression of the ipsilateral external jugular vein by the physician.

Objectives: (primary and important secondary objectives)

This study seeks to pilot an evaluation of whether an external jugular vein compression collar approved by the FDA for contact sports can provide symptomatic relief of venous pulsatile tinnitus. Furthermore, the study will pilot quality of life impacts of the device. Study Design:

This is a non-blinded, interventional, prospective single cohort pilot study in which participants will be asked to evaluate the effect of wearing the collar, if any, on tinnitus symptoms. Secondary effects such as adherence, comfort, and quality of life while wearing the device will also be evaluated.

#### Setting/Participants:

This study will recruit 20 participants complaining of pulsatile tinnitus who are patients at the UNC Meadowmont ENT outpatient clinic. Inclusion criteria will include those patients identified to have pulsatile tinnitus without a medical or surgical treatment upon thorough evaluation by the ENT service. Exclusion criteria will be those with non-pulsatile tinnitus, age, cerebral infarction (blockage or narrowing in the arteries supplying blood and oxygen to the brain) or severe head trauma, medical contraindications to restriction of blood outflow via the internal jugular veins, glaucoma, hydrocephalus, recent penetrating brain trauma (within 6 months), known carotid hypersensitivity, known increased intracranial pressure, idiopathic intracranial hypertension, known intracranial vascular malformation, central vein thrombosis, any known airway obstruction, or those not tolerating initial fitting of the collar.

#### Study Interventions and Measures:

The intervention device is marketed as the Q Collar, a light jugular vein compression device FDA approved for use in contact sports for individuals above the age of 13. Main study outcomes will be degree of relief upon application of collar, sustainment of relief with home use of the collar, and quality of life metrics administereed at the beginning and end of the study.

Study Title	PROTOCOL SYNOPSIS Internal Jugular Vein Compression Collar for Novel Symptomatic Treatment of Venous Pulsatile Tinnitus			
Funder	Departmental Funds			
Clinical Phase	Pilot Study			
Study Rationale	Venus pulsatile tinnitus is a subtype of tinnitus that is refractory to medical treatment. Its defining symptom is patient perception of a whooshing sound in time with the heartbeat, and its characteristic diagnostic sign is relief of symptoms when the internal jugular vein is lightly compressed by the physician during examination. This study seeks to apply the defining diagnostic findings to treatment through use of a internal jugular vein compression collar approved by the FDA for contact sports.			
Study Objective(s)	Primary			
	• To determine if an internal jugular vein compression collar significantly relieves symptoms of venous pulsatile tinnitus.			
	Secondary			
	To determine quality of life impacts			
Test Article(s) ( If Applicable )	The Q-Collar is a non-invasive device intended to be worn around the neck of athletes aged 13 years and older during sports activities to aid in the protection of the brain from effects associated with repetitive sub-concussive head impacts.			
Study Design	Interventional single cohort pilot study. Data collected at original visit vai completion of tinnitus intensity and QOL scales, daily during 2-4 week follow up, and at follow up visit. All data collect through REDCAP administered scales into REDCAP password protected database			
Subject Population	Inclusion Criteria			
key criteria for	1. Subjects age 18 and older			
Inclusion and	2. Subjects are diagnosed with pulsatile tinnitus			
Exclusion:	3. Subjects are patients at UNC ENT Meadowmont outpatient clinic.			
	Exclusion Criteria			
	1. Known risk factors for or existence of intracranial or intraocular hypertension, listed in detail in study protocol.			
Number Of Subjects	20			
Study Duration	Each subject's participation will last 2 weeks			

Study Phases Enrollment Study Treatment Follow-Up	
 
Participants meeting inclusion/exclusion criteria at UNC
 
Meadowmont will be invited to participate. Those who consent will be fitted with the collar. Then, the at home treatment phase will begin where they report on collar efficacy. Finally, a follow up visit will be conducted to complete exit surveys.
 
	
Efficacy Evaluations	Significant improvement in tinnitus symptoms while wearing collar.	
Safety Evaluations	At intiial visit, team clinician will supervise collar fitting and evaluate for significant pain, discomfort, or adverse effect which will halt participation for that participant and be recorded. During at home study phase, participants will report any adverse effects with their daily recording of symptomatic efficacy.	
Statistical And Analytic Plan	One sided t test on tinnitus intensity while wearing collar vs. while not wearing collar will evaluate primary endpoint of collar relief efficacy. ANOVA analysis of intensity differences will elucidate effect of time, if any. One sided t test will evaluate secondary endpoints of quality of life	
DATA AND SAFETY MONITORING PLAN	Faculty mentor [name] is monitoring all safety related aspects. These include the evaluation of the initial collar fit, collar use education, and reporting of adverse events during at home period.	

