# 2.2 Secondary Objectives (or Aim)

The secondary objectives are to:

- Determine if the collar effect varies with time
- Evaluate changes in quality of life as a result of collar use
- Compare home use with in clinic use

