# 3.2.2 Total Number of Study Sites/Total Number of Subjects Projected

The study will be conducted at approximately 1 investigative site in the United States. This site is the UNC Meadowmont ENT outpatient clinic.

Recruitment will stop when approximately 20 subjects are recruited. It is expected that approximately 22 subjects will be enrolled to produce 20 evaluable subjects.

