# 5.2 Efficacy Evaluations

#### 5.2.1 Diagnostic Tests, Scales, Measures, etc.

- Primary endpoint: symptom relief
  - Tinnitus aural intensity scale before and after collar administration at each visit and once daily for with collar and without collar intensity
- Secondary endpoint: QOL Impact
  - Tinnitus Handicap Index (Once at beginning of study, once at end)
  - Patient Reported Outcome Measurement Information System (PROMIS) scales in depression, anxiety, physical function, and satisfaction
- Secondary endpoint: Temporality
  - Aural intensity scale submissions will be plotted and compared over time course of study
- Secondary endpoint: Homes vs. clinic use
  - Supervised tinnitus intensity scale measurements will be compared to at home measurements to evaluate if perception of symptomatic intensity varies with environment

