#### 6.3.2 Efficacy Analysis

The primary analysis will be based on an intention to treat approach and will include all subjects who complete the study.

The primary efficacy endpoint will be the change in tinnitus intensity with and without the collar, averaged within and across each patient's completion of the tinnitus scales. This means that there will be 16 paired collar and no collar measurements per patient, one at each clinic visit and one each day during the 14 day intervening period. The significance of this change will be evaluated using a unidirectional t-test.

Secondary endpoints will include the following:

- Temporality of symptom relief
  - Subjects with and without collar scores will be averaged for each day of the study, ANOVA testing will evaluate for the presence of a significant time component.
- Supervised vs. unsupervised use
  - The mean relief recorded at the first and second visit will be averaged and compared avross patients with the mean relief recorded during at home use using a bidirectional t test.
- QOL impacts
  - Evaluated for each scale using bidirectional t test

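### Sustained relief is listed as a main outcome but is neither defined nor estimated with an interval, and the only test over time is an omnibus ANOVA that cannot show it

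*Combined protocol and SAP*

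**What the plan says.** The Abstract (Study Interventions and Measures) names three kinds of main outcome, one of which is "sustainment of relief with home use of the collar". The body ranks time lower and words it differently. The secondary objective in section 2.2 is to "Determine if the collar effect varies with time", and sections 5.2.1 and 6.2 also place the time effect among the secondary endpoints.

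The analysis in section 6.3.2 has two parts: "Subjects with and without collar scores will be averaged for each day of the study", and then "ANOVA testing will evaluate for the presence of a significant time component". The synopsis (Statistical and Analytic Plan) applies it to differences: "ANOVA analysis of intensity differences will elucidate effect of time, if any". No contrast, direction, margin, interval or participant term is stated.

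Three other planned items bear on the question:
- Section 5.2.1: "Aural intensity scale submissions will be plotted and compared over time course of study".
- Section 6.3.2, supervised versus unsupervised use: relief at visits 1 and 2 is averaged and "compared avross patients with the mean relief recorded during at home use using a bidirectional t test".
- Section 6.3.2, primary analysis: the average over 16 paired ratings includes the 14 home days.

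Section 3.2.2 expects that "approximately 22 subjects will be enrolled to produce 20 evaluable subjects".

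**The concern.** Sustainment is a claim that an effect is still there later on. An omnibus test of equality across days is poorly matched to it in both directions. If it is not significant, that is absence of evidence for change, not evidence of maintenance. If it is significant, the test alone does not say whether relief faded, grew or fluctuated. The test also spreads its power over every possible day-to-day pattern, while the pattern that matters most here is a steady decline.

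At stake is whether the pilot can say anything quantitative about relief late in home use. As written, it could yield a significant average benefit and a non-significant time test even though relief had gone by the end, and the plan provides no interval that would expose this.

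**Working it through.** **Plan's own figure.** None exists for the time analysis. Section 6.4 covers the principal endpoint only. Its substituted line gives (1.96 + 0.8416)² × (4 + 4) / 4 = 15.70, against the stated 15.86. That line divides by 2² although the text names a 1-point effect, which is a separate matter.

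**Inputs from the documents.** 20 evaluable participants (3.2.2); 14 home days, study days 2-15 (Table 1); 1-point minimum effect and alpha 0.05 (6.4).

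**Assumptions not in the documents.** Independent day-to-day rating SD s = 1.2 (range 0.8 to 1.6) in each condition, so a daily difference has within-participant variance 2s² = 2.88 (1.28 to 5.12). The analysis uses home days only, on differences, with participants as blocks, complete data and the same underlying trend in everyone. This favours the plan, because 6.3.2 states no participant term.

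**Omnibus test, linear fade from 1 to 0.** The sum of squared deviations of the 14 daily means is 1.346. The noncentrality is λ = 20 × 1.346 / 2.88 = 9.35 with 13 and 247 df.
- Power is about 0.44.
- At s = 0.8, λ = 21.03 and power is 0.86. At s = 1.6, λ = 5.26 and power is 0.24.

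**Mean participant slope, same fade.** The slope is −1/13 = −0.0769 per day, and the sum of squared centred days is 227.5. The standard error is √(2.88 / 227.5 / 20) = 0.0252. The noncentrality is 0.0769 / 0.0252 = 3.06 with 19 df.
- Two-sided power is about 0.83 (0.59 at s = 1.6; 0.99 at s = 0.8).

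**Other fades.**
- Halving, 1 to 0.5: omnibus 0.12 (0.09 to 0.24), slope 0.31.
- 2 to 0: omnibus 0.99 at s = 1.2 and 0.86 at s = 1.6.

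**Cross-check with the plan's SD of 2.** This uses all 16 time points and a repeated-measures ANOVA. The assumed correlation between the paired ratings is 0, 0.5 or 0.8, and between-day correlation of relief runs from 0 to 0.7. For a fade from 1 to 0:

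| Pair correlation | Omnibus | Linear trend |
|---|---|---|
| 0 | 0.16-0.56 | 0.45-0.92 |
| 0.5 | 0.33-0.91 | 0.74-1.00 |
| 0.8 | 0.78-1.00 | 0.98-1.00 |

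A fade from 2 to 0 gives the omnibus test 0.66 or more throughout. A one-way ANOVA that ignores the participant gives about 0.00 to 0.78 for the fade from 1 to 0.

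**Do the other planned analyses cover it?** Take a linear loss from 1 to 0 over the 16 points.
- Home versus clinic: the clinic mean is (1 + 0)/2 = 0.5 and the home mean is also 0.5. The expected difference is 0.00, so the test rejects only at its 0.05 level.
- Primary average: mean relief is still 0.5. The one-sided test is significant with probability 0.23 to 0.90 (pair correlation 0 to 0.8, between-day correlation 0.3 to 0.7).
- Daily means and plot: descriptive, with no interval or decision rule.

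**Precision available.** The change in mean relief from days 2-8 to days 9-15 has a 95% half-width of 2.093 × 1.2 × √2 × √(2/7) / √20 = 0.42 (0.28 to 0.57 over the SD range). If true change varies between participants with an assumed SD of 0.5 to 1.5, this becomes 0.48 to 0.82. Relief on a single day has half-width 2.093 × SD / √20, which is 1.32, 0.94 or 0.59 for difference SDs of 2.83, 2.00 and 1.26. A seven-day mean would be no wider under the same variance.

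**The case against.** The strongest reply is that the body asks only whether the effect varies with time, and an ANOVA for a time component fits that question. Sustainment as a main outcome rests on one Abstract sentence, and it can also be read as relief carrying over from clinic to home, which has its own t test. Daily means are planned, so relief on each late home day can be read off, and the plot would show the direction of any change.

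Much of this stands. Time is secondary in the body, and the ANOVA is not the only analysis that touches the question. What remains is that no interval accompanies the late-day means and that the home-versus-clinic test cannot see a linear fade.

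A reader might go further and infer that a non-significant ANOVA will be reported as sustained relief, or carried into the grant application as evidence of durability. The documents say neither. Section 2 ties the grant to evidence of efficacy and does not mention durability. The missing decision rule leaves the possibility open, no more.

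The power figures also depend on an SD that no document gives. Over its range the omnibus test goes from usually missing a 1-point fade to usually finding it.

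**Conclusion.** The point holds in a limited form. Sustained relief is undefined, has no planned interval estimate, and is tested only by an omnibus ANOVA that cannot establish maintenance whatever its power. For a 1-point linear fade to 0 over the home days, that test has power about 0.44 (0.24 to 0.86), against 0.83 (0.59 to 0.99) for a participant-level slope, under the assumed rating SDs, participant blocking, complete data and a common trend.

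It would be too strong to say that the plan would miss a disappearance of relief in general. A 2-point fade would usually be detected, and so would a 1-point fade if the paired ratings correlate at about 0.8. The change is worth making because a better-targeted analysis is available from data already being collected. The primary analysis is not affected.

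**What to change.** In section 6.3.2, under temporality, compute each participant's daily no-collar minus collar difference and report with 95% CIs:
- (a) mean relief over home days 9-15;
- (b) the mean participant slope of relief over home days 2-15, as the test of time.

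The change from days 2-8 to days 9-15 can be added as an optional summary; the split is a convention. Keep the ANOVA as supportive, with the participant as a term. State that a non-significant time effect will not be reported as sustained relief. Align the Abstract with sections 2.2 and 6.2 on whether sustainment is a main or a secondary outcome.

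The cost is a few lines of analysis text and two or three rows in a table, with no new data or visits. The downside is that in 20 people the intervals may be wide enough that the honest answer on sustainment is inconclusive.

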#### **EXAMPLE: TABLE 1: SCHEDULE OF STUDY PROCEDURES**

Study Phase	Screening through EPIC	Initial consenting and fitting visit	Home Use (Daily for 14 days)	Follow up visit
Visit Number	N/A	1	N/A	2
Study Days	0	1	2-15	16
Informed Consent/Assent		Х		
Review Inclusion/Exclusion	Х			
Criteria				
Demographics/Medical		Х		
History				
Fit Collar		Х		
Adverse Event Assessment		Х		
QOL Data		Х		Х
Symptom Relief Data		Х	Х	Х
Adherence/Usage Data			X	
Adverse Event Reporting			X	

#### 1 BACKGROUND INFORMATION AND RATIONALE

Section 1 should be no more than 3-5 pages. Refer the reader to the applicable grant, or attached literature references for more detailed information.

#### Introduction

Tinnitus is a medical condition with a wide variety of causes that is characterized by the perception of sound, often described as ringing or buzzing, without an external stimulus.1 It is extremely common, and has a prevalence in the United States ranging from 10% to 15% of the population.2 Persistent tinnitus can have a highly negative impact on quality of life, with individuals suffering from the condition manifesting higher rates of anxiety, depression, and lowered self esteem^3-5. Pulsatile tinnitus is a specific subtype of tinnitus with limited treatment options. It is defined as a "whooshing" sound that pulsates in rhythm with the patient's heartbeat and generally manifests unilaterally. Pulsatile tinnitus affects over 10% of the total tinnitus population, and it has a variety of both vascular, specifically venous, and nonvascular causes. Unlike traditional tinnitus, medication is ineffective for most causes of pulsatile tinnitus. The provocative physical exam test for venous pulsatile tinnitus consists of the physician lightly compressing the internal jugular vein ipsilateral to the side of symptoms. For patients with any venous cause of pulsatile tinnitus, symptoms will be relieved upon compression of the ipsilateral internal jugular vein and return when pressure is released by the examiner, a diagnostic finding with 93% sensitivity. Given that the provocative exam finding for venous pulsatile tinnitus is relief of symptoms while compressing the neck, and that in many cases effective treatment options are limited for this condition, it is the goal of this study to test a FDA approved internal jugular vein compression collar as a symptomatic treatment for patients with this condition. By applying and sustaining the compression technique used by physicians on exam, it is hypothesized that this collar will achieve significant, perhaps even complete reduction in patient symptoms.

#### 1.1 Name and Description of Investigational Product or Intervention

The current FDA approved internal jugular vein compression collar, marketed as the Q collar, is manufactured by Q30 Innovations Home. It is designed to be worn around the neck of individuals aged 13 and older. It functions by lightly compressing the internal jugular vein's bilaterally, safely increasing intracranial volume and intracranial pressure. The FDA approved neck collar device is made of a thermoplastic elastomer that is specifically fitted to an individual to provide mild internal jugular vein compression. The product was developed and confirmed with ultrasonography to confirm appropriate fit and compression of the vein based on an athlete's neck circumference.

#### 1.2 Findings from Non-Clinical and Clinical Studies

(This section is only applicable for drugs, biologics and devices)

#### 1.2.1 Non-Clinical Studies

The landmark paper by Smith et al. (2012) and Turner et al. (2012) demonstrated significant reduction in axonal injury following internal jugular vein compression in a rodent concussion model and this catapulted the translatable research specifically in concussion mitigation. Interestingly during rodent behavioral testing in the application to blast concussive injury, a potential protective benefit of IJV compression against hearing injury was discovered by the faculty preceptor of this project, [name], and his team. Through conversations with the student researcher and with colleagues at UNC otolaryngology, including faculty attending [name], the collar was identified as a potential intervention for venous pulsatile tinnitus.

#### 1.2.2 Clinical Studies

The use of jugular compression collars (Q-collar) during physical activity has recently been shown to reduce white matter alterations associated with head impact exposure in male and female athletes in sports including football, hockey, and soccer. Ongoing trials have demonstrated improvements in concussion biomarkers through clinical and radiographic measures.

#### 1.3 Relevant Literature and Data

Pulsatile Tinnitus: Overview, Pathophysiology, Diagnosis

Pulsatile Tinnitus is the auditory perception of rhythmic noises in time with the heartbeat. It can be either vascular or nonvascular in origin, and vascular presentations are divided into venous and arterial etiologies. In vascular etiologies, the symptomatic presentation is a consequence of turbulence in vasculature near the cochlea, hence the synchronization with pulse. This condition can have significant adverse effects on patient quality of life, leading to insomnia, difficulty concentrating, impaired audition, and mental health deterioration. Venous abnormalities are the most common causes of pulsatile tinnitus, particularly structural and flow abnormalities in one or multiple intracranial or extracranial venous structures secondary to intracranial hypertension or anatomical variation. Non-invasive imaging is an effective means of diagnosing pulsatile tinnitus, successfully identifying relevant phenomena in 40% to 70% of cases. Furthermore, physical exam alone can distinguish venous causes from other ideologies of pulsatile tinnitus. Specifically, relief of symptoms upon temporary manual neck compression of the ipsilateral IJV detects venous etiology with 93% sensitivity, a finding that is replicated with less sensitivity by a Valsalva maneuver or by turning the patient's head toward the side lateralizing with pulsatile tinnitus.9-10

#### Etiologies of Venous Pulsatile Tinnitus

Venous pulsatile tinnitus is caused by a broad differential of specific etiologies. All etiologies involve disturbed flow of an internal jugular vein and/or one of the veins or sinuses that drain into it.30 The turbulent flow is conducted by the skull base and mastoids to the cochlea, resulting in the perception of pulsating sound. Broadly, these etiologies and their treatments can be classified by location of the abnormality: the lateral sinuses, emissary veins, jugular bulb, and internal jugular vein. For cases in which the underlying etiology cannot be identified and corrected, there are few options for symptomatic

management. Cognitive behavioral therapy, meditation, and sound machines have all been employed for symptomatic management with limited success.

